11.12.4.1 Missing values

Data on exposure and especially the potential confounders may be missing for a proportion of the study participants. These data are often collected from existing medical records, vaccine registries, etc. which existed before the modified SARI episode, and it seems reasonable to assume that whether the data is missing is independent of the RSV status during the modified SARI episode. Assuming that the described missing data mechanism holds, performing a complete case analysis (CCA) will not lead to biased results. The primary analysis will therefore be a CCA, dropping records with missing information for the outcome, exposure of interest or the covariates. In case >10% of the cases and controls have missing covariate information, CCA is likely to be inefficient and alternatives such as multiple imputation and augmented CCA will be explored. A sensitivity analysis will be carried out comparing results from CCA (where records with missing data are dropped) and full set analysis (with imputed data).

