- Vaccinated with RSV vaccine during the study period of interest': vaccinated with exposure of interest: e.g. single dose/primary vaccination/at least one dose of the RSV vaccine during the epidemiological year(s) of interest, within the appropriate timeframe for the product to be **effective** prior to modified SARI symptom onset.
- Unvaccinated with RSV vaccine during the study period of interest': did not receive any RSV vaccine during the epidemiological year(s) of interest.
- 'Recently vaccinated with RSV vaccine during the current RSV season': Vaccinated with *exposure of interest: e.g. single dose/primary vaccination/at least one dose* of the RSV vaccine during the epidemiological year(s) of interest, within the appropriate timeframe for the product to be **ineffective** prior to modified SARI symptom onset.
- 'Other':

additional vaccine exposure definitions might be defined depending on the real-life use of the RSV vaccines.

Data sources, data collection

The study uses a combination of primary (e.g., specific laboratory results, vaccine cards) and secondary data sources (e.g., existing hospital databases, vaccine registries and linked data).

After study enrolment, data will be collected directly from the patient or by consulting medical records. Information to be collected at minimum includes date of modified SARI symptom onset, date of hospitalisation, respiratory specimen testing results, and information on the potential confounders and effect modifiers.

Exposure status, RSV vaccine information and date(s) of vaccination(s) will be ascertained by consulting vaccination registries, vaccination cards or medical records (depending on the country and region). Where needed, treating physician or other health care professionals will be contacted to obtain additional information.

Context information on national/regional vaccination recommendations and RSV vaccine label information will be collected from external sources.

Covariates

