Clusters will be defined at the hospital network (Study Contributor) level. If some networks have hospitals that are very different (e.g. geographically separated), then clustering could be defined at the hospital level for these networks. However, similarities between these hospitals may remain due to being part of the same hospital network, in which cases these would not be treated as being independent of each other.

An important choice is whether the exposure odds ratios are desired to have a subject-specific (SS) or population-averaged (PA) interpretation. The SS OR compares odds of vaccination among the RSV-positive cases to the odds of vaccination among the RSV-negative controls from the same Study Contributor (conditional on other covariates) and necessitates the inclusion of a fixed-effect of a random-effect term for Study Contributor or via a meta-analysis. The PA OR compares the odds of vaccination among RSV-negative controls across the Study Contributors (conditional on other covariates) and is commonly obtained from a generalised estimating equation (GEE) model. Care should be taken with regards to method selection (estimators for point-estimates and standard errors) to avoid biased VE estimates when the clustering variable is a potential confounder.

Sensitivity analyses will be conducted as appropriate. A complete and detailed statistical analysis plan (SAP) will be developed prior to the conduct of the analysis.

Reporting

Progress reports will be prepared every two months. Interim analyses will be planned as appropriate. A final study report will be written. Interim reports and the final report will be submitted to the European Medicines Agency (EMA) and other competent regulatory bodies (e.g., Medicines and Healthcare products Regulatory Agency (MHRA), U.S. Food and Drug Administration (FDA) by the marketing authorisation holder (MAH) to meet regulatory requirements.

Data management

Data collected at Study Contributors will be checked for quality and transferred to a dedicated, secured central server hosted by P95. A data management plan (DMP) will be written prior to the start of the data collection. The DMP describes all functions, processes, responsibilities and specifications for data collection, cleaning, and validation.

An expert consensus group to classify exposure groups will consist of members of the Study Teams. In case of disagreement, the Independent Scientific Committee (ISC) of id.DRIVE will be consulted.

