11.7 Identification of modified SARI patients

Modified SARI patients will be identified based on the 'modified SARI definition' (section 13.6.2) either prospectively (e.g., during consultation in the emergency department (ED) or at admission to an infectious disease or internal medicine hospital ward) or retrospectively by hospital database search or from respiratory samples sent to the virology laboratory.

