11.8.2 Exposure ascertainment

Information on all prior RSV vaccine doses will be collected. Vaccination status, vaccination date, vaccine dose and vaccine name and brand information are required. Depending on the Study Contributor, the source for exposure ascertainment will be different and may include vaccination registries, medical records, or vaccination cards. Information on the source documentation of the exposure ascertainment will be collected.

Patients that cannot be classified into one of the exposure categories (i.e., their vaccination status is unknown) will be excluded.

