- In Germany there is no vaccine registry available, and paper vaccination cards are used for documentation. In some cases, the vaccination card may not be available as a physical document at the time of hospital admission, thus, provision of the vaccination data card may be foreseen by relatives, which can be challenging. In addition, there is a chance of incomplete data because of unreadable handwriting on vaccination cards. Therefore, misclassification of vaccination status may be greater for data collected in German sites.
- The PROMISE generic RSV VE protocol recommends the exclusion of persons with a contraindication to the RSV vaccine being studied, in order to only capture the eligible population. Such patients are not excluded from the present study, as vaccine contraindications cannot be collected. However, numbers are expected to be small.
- Despite RT-PCR's high specificity and sensitivity, diagnostic inaccuracies pose potential bias, influenced by factors like sampling technique, specimen type, number of specimens [17, 18], and timing. In RSV RT-PCR, declining sensitivity over time may yield more false negatives among vaccinated, overestimating VE. Sensitivity analyses, such as varying time between symptom onset and sampling, as well as addition of pre-admission rapid antigen testing, will

explore potential misclassification bias. Study staff follow guidance for proper specimen collection, ensuring a robust testing procedure.

- Unaccounted potential confounders in this study, such as ethnicity and socio-economic status, could lead to overestimated VE when certain groups are less likely to be vaccinated. TNCC studies, limited to those accessing healthcare or hospitalised, may not generalise to disadvantaged groups with poor access or nursing home residents, affecting result applicability.
- This study does not measure frailty, an important potential effect modifier of VE. Frailty has been shown to affect immune responses in older adults to vaccines for infections such as influenza, shingles and pneumococcus [19]. Frailty, impacting immune responses in older adults, lacks a consensus definition and measurement method. Given the study's focus on the general population and frailty's complexity, we collect information on related variables like age, body mass index (BMI), long-term care residence, and chronic conditions instead of directly measuring frailty.

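### The protocol does not require equal retrieval of vaccination data in cases and controls, or classification masked to RSV status, so the premise behind the complete-case VE is unprotected

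*Protocol*

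**What the plan says.** Section 11.12.4.1 of the protocol notes that exposure and confounder data are often taken from medical records and registries that existed before the episode. From this it concludes that "it seems reasonable to assume that whether the data is missing is independent of the RSV status during the modified SARI episode". Provided that mechanism holds, it states that "performing a complete case analysis (CCA) will not lead to biased results", and it draws the consequence: "The primary analysis will therefore be a CCA, dropping records with missing information for the outcome, exposure of interest or the covariates". Section 11.8.2 adds: "Patients that cannot be classified into one of the exposure categories (i.e., their vaccination status is unknown) will be excluded".

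Other sections describe how vaccination status becomes known. The abstract (section 8, data sources) places data collection after enrolment and says: "Where needed, treating physician or other health care professionals will be contacted to obtain additional information". Section 13 explains that Germany has no vaccine registry and that "provision of the vaccination data card may be foreseen by relatives, which can be challenging". Section 11.7 allows patients to be identified prospectively or "retrospectively by hospital database search or from respiratory samples sent to the virology laboratory". The abstract (data management) says: "An expert consensus group to classify exposure groups will consist of members of the Study Teams". It refers disagreements to the Independent Scientific Committee.

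The only separation that the protocol states is in section 11.11, which keeps vaccine companies away from data collection and analysis. That is not masking to case or control status.

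**The concern.** A record that exists before the illness is not thereby retrieved. Independence from RSV status has to hold for retrieval, and retrieval here takes place after enrolment by people who may know the RSV result. For patients found retrospectively the result will normally already exist. For prospective patients the order is open, because specimens may be taken from 10 days before to 72 hours after admission.

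Two things must happen together for the odds ratio to be distorted. Retrieval must succeed at different rates in vaccinated and unvaccinated patients, and that difference must itself differ between cases and controls. The first is plausible. Section 13 says that date, dose number and brand are mandatory for a participant to be retained, and these can be found only for someone who was vaccinated. The second needs only unequal effort, which nothing in the text rules out. What is at stake is the primary VE estimate. Once records have been sought unevenly, the analysis cannot restore them.

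**Working it through.** The protocol states no missingness or retrieval rates, so there is no figure to reproduce. The check uses the selection formula for a case-control odds ratio.

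**Inputs.** VE = (1 − OR) × 100% (section 11.12.4). All retrieval probabilities and the true VE are assumptions.

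**Formula.** Let s be the probability that exposure is known, with first index v or u (vaccinated, unvaccinated) and second index 1 or 0 (case, control).

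k = (s_v1 × s_u0) / (s_u1 × s_v0), and OR in complete cases = OR true × k.

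**Results with a true VE of 70% (OR 0.30).**

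| Retrieval depends on | s_v1 | s_u1 | s_v0 | s_u0 | k | VE read |
|---|---|---|---|---|---|---|
| RSV status alone | 0.95 | 0.95 | 0.80 | 0.80 | 1.000 | 70.0% |
| Vaccination alone | 0.95 | 0.80 | 0.95 | 0.80 | 1.000 | 70.0% |
| Both, as a simple product | 0.855 | 0.72 | 0.95 | 0.80 | 1.000 | 70.0% |
| Both: vaccinated status found more often in cases | 0.95 | 0.90 | 0.90 | 0.90 | 1.056 | 68.3% |
| same | 0.95 | 0.90 | 0.85 | 0.90 | 1.118 | 66.5% |
| same | 0.95 | 0.90 | 0.75 | 0.90 | 1.267 | 62.0% |
| Both: unvaccinated status found more often in cases | 0.95 | 0.95 | 0.95 | 0.85 | 0.895 | 73.2% |
| same | 0.95 | 0.95 | 0.95 | 0.75 | 0.789 | 76.3% |

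For example, 0.95/0.75 = 1.267 and 1 − 0.30 × 1.267 = 0.620. In the other direction, 0.75/0.95 = 0.789 and 1 − 0.30 × 0.789 = 0.763. With a true VE of 50% the same two extremes read 36.7% and 60.5%.

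**Would crude missingness reveal it?** Take the 66.5% row and assume 20% coverage in controls. The odds of vaccination in cases are 0.25 × 0.30 = 0.075, so 0.075/1.075 = 7.0% of cases are vaccinated.

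- Missing in cases: 1 − (0.070 × 0.95 + 0.930 × 0.90) = 9.7%.
- Missing in controls: 1 − (0.20 × 0.85 + 0.80 × 0.90) = 11.0%.

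The two are nearly equal, yet VE is off by 3.5 points. In the first row of the table, 5% of cases and 20% of controls have missing exposure, and there is no bias.

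**Planned safeguards.** The 10% trigger in 11.12.4.1 concerns covariates and is argued from efficiency. The comparison with imputed data does not say that exposure is imputed, and 11.8.2 excludes unknown status. Standard imputation would in any case not correct missingness that depends on the unseen exposure. The attrition diagram in 11.12.2 is by reason for exclusion, with no split by case status stated.

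**The case against.** A reader might infer that vaccination data are chased and classified after the RSV result is known, by people who are not masked to it. The protocol does not say that. It fixes no order for prospective patients and is silent on masking. This is a Master Protocol that leaves collection detail to Study Contributor-specific protocols, the data management plan and the data validation plan, none of which is at hand. Nor does it say that the consensus group adjudicates doubtful individual records; its task could be to define exposure categories. No text shows that RSV-positive patients are pursued harder. Section 11.8.2 asks for the same exposure items from everyone, and the two-weekly data queries have no stated RSV-dependent trigger.

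A reader might also infer that VE is necessarily underestimated. That holds only if extra effort in cases recovers mainly vaccinated records. Contacting a physician can settle either status, and recovery in equal proportion gives k = 1. The card problem is described only for Germany, one of four named countries, so study-wide rates as uneven as those assumed may be too pessimistic.

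The claim of no bias is also conditional, and the German difficulty is disclosed, although as misclassification.

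These points limit the concern to an unprotected premise. They do not remove it: the reason given for the premise is that the records predate the episode, and this does not address retrieval. Uniform retrieval and masked classification are conduct rules that an analysis plan cannot supply afterwards.

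**Conclusion.** The point holds in limited form. The protocol rests its primary analysis on missingness being independent of RSV status, gives a reason that does not establish this, and states no rule that would protect it. Complete-case VE may be biased in either direction, but only if retrieval depends jointly on RSV status and vaccination, beyond a simple product of the two. The range of about 62% to 76% around a true VE of 70% illustrates what uneven retrieval could do under the assumed rates. It is not an estimate of what will happen in this study. Correction is advisable because it is cheap and must be in place while data are collected.

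**What to change.** In section 11.8.2, require two things:

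- **(a) Equal retrieval.** The same retrieval steps and the same number of attempts apply to every participant with missing exposure data. They are triggered only by that missingness and never by the RSV result.
- **(b) Masked classification.** The consensus group receives exposure records with the RSV result removed.

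In section 11.12.4.1, base the independence premise on (a) and (b) instead of on the age of the records.

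In the attrition diagram (11.12.2), report exclusions for unknown exposure by case or control status, source of ascertainment and Study Contributor. Label this a descriptive diagnostic. It cannot serve as a test of the premise, because near-equal missingness can hide bias and unequal missingness can be harmless.

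The cost is a few sentences, one data extract without the RSV field, and slightly more pursuit of control records.

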11.12.4.2 Sensitivity analyses

Multiple sensitivity analyses will be performed. Alternative statistical models may be used that differ from models used for the primary and secondary objectives. Additional sensitivity analyses that can be conducted include:

- exploring the effect of time between symptom onset date and swab date,
- exploring the effect of time between symptom onset date and hospitalisation,
- exploring the effect of time between hospital admission and swab date,
- exploring the effects of different modified SARI definitions (id.DRIVE case definition¹⁸, World Health Organisation [WHO]-RSV case definition¹⁹),
- exclusion of patients who have received monoclonal antibodies and other RSV products for either treatment or pre- or post-exposure prophylaxis prior to hospitalisation if there is significant use thereof in the population,
- exploring unmeasured confounding or biases through negative control methods: negative control exposure and/or negative control outcomes (e.g., exclusion of test-negative controls that tested positive with RADT in the 10 days prior to hospital admission),

¹⁹ A World Health Organisation (WHO)-expanded definition of RSV-SARI (severe disease – defined as requiring hospitalisation AND acute – defined as onset within the last 10 days AND respiratory infection – defined as having at least one of the following: shortness of breath or cough) will be used in sensitivity analyses. [Source: https://www.who.int/teams/global-influenza-programme/global-respiratory-syncytial-virus-surveillance/case-definitions]

¹⁸ An id.DRIVE definition of SARI (defined as requiring hospitalisation with a suspicion of a respiratory infection with symptom onset within the last 14 days prior to hospital admission, having at least one of the following symptoms: cough, shortness of breath, fever (\geq 38 C°) or sudden onset of anosmia, ageusia or dysgeusia) will be used in sensitivity analyses. This SARI definition is modified from the latest ECDC case definition (specifying "suspicion of respiratory infection"). [EUROPEAN CENTRE FOR DISEASE PREVENTION AND CONTROL (2023). Core protocol for ECDC studies of COVID-19 vaccine effectiveness against hospitalisation with Severe Acute Respiratory Infection, laboratory-confirmed with SARS-CoV-2 or with seasonal influenza - Version 2.0. Available from: https://www.ecdc.europa.eu/en/publications-data/core-protocol-ecdcstudies-covid-19-vaccine-effectiveness-against-0 [Accessed: 17-08-2023]].

- the effect of redefining the positive case group, by including only RSV tested-positive cases without a coinfection, and
- the effect of patients having ≥ 2 laboratory-confirmed RSV infections in the current season.

All sensitivity analyses will be pre-specified in the SAP.

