Variables that are potential confounders and/or effect modifiers will be collected at Study Contributors. These include: age, gender, history of selected morbidities of interest (e.g., asthma, lung disease, cardiovascular disease, and immunocompromising conditions)⁷, vaccination against other respiratory pathogens (severe acute respiratory syndrome coronavirus 2 [SARS-CoV-2], influenza, *Streptococcus pneumoniae*), history of prior RSV infection, prior modified SARI hospitalisation(s), pregnancy (and term), smoking history, history of anti-RSV antibodies received either as prophylaxis

⁷ Definitions of the comorbidities of interest will be specified in detail as part of the electronic case report form (eCRF).

or treatment for the current or previous modified SARI episodes, body mass index (BMI), and long-term care facility residence.

RSV testing

Reverse transcription polymerase chain reaction (RT-PCR) or another ribonucleic acid (RNA) amplification system with at least the same sensitivity as RT-PCR (e.g., transcription-mediated amplification [TMA]) will be required to confirm an RSV infection. RT-PCR assays must be used for the detection of at least RSV, SARS-CoV-2, and influenza. Information on the RSV subtypes will be collected to the extent possible, preferably on all confirmed RSV cases when sample quality allows.

Respiratory sampling should preferably be done in both the nasopharynx and oropharynx, using a stiff oropharynx swab or a flexible nasopharynx swab. Additional respiratory specimens are accepted (e.g., saliva/saline mouth wash, sputum, bronchoalveolar lavage, or aspirates), when collected as part of patient diagnostic work-up.

It is recommended that specimens are collected *within 10 days prior to and up to 72 hours after hospital admission* for analysis of the primary objective. All test-negative tests will be re-tested at hospital admission.

Sample size

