	If yes, brand, date, and source of information
Vaccination history influenza	Binary, within 12 months prior to the modified SARI hospital
	admission
	If yes, brand, date, and source of information
Vaccination history	Binary, at least one vaccination in the past
pneumococcus	If yes, brand, date, and source of information
Long-term care facility	Binary, if no, specification of residential situation before
residence	hospitalisation: 'Home', 'Home with nursing care', 'Transfer from
residence	another hospital', 'Rehabilitation centre', 'Nursing home',
	'Other', 'No information'
History of RSV in the current	Binary
season before symptom onset	If yes, date.
leading to this hospitalisation	n yes, date.
Prior modified SARI	Binary,
hospitalisation episode in	If yes, time since most recent prior modified SARI hospitalisation
previous 12 months	n yes, time since most recent phot mounied shar hospitalisation
Month and year of prior SARI	Month and year
episode	
Respiratory support	'None', 'Oxygen therapy', 'Non-invasive ventilation', 'Invasive
	mechanical ventilation', 'Extracorporeal membrane oxygenation
	(ECMO)', 'No information'
ICU admission	Binary, date of admission, date of discharge
In-hospital death	Binary, date of hospital discharge or in-hospital death
Post-discharge destination	'Home', 'Home with nursing care', 'Transfer to another hospital',
	'Rehabilitation centre', 'Nursing home or other long-term care
	facility', 'Other', 'No information'
Length of hospital stay	Days, continuous
Treatments received during	'Antibiotics', 'Antiviral drug(s)', 'Corticosteroid(s)', 'Immune
hospital stay for the	modulator(s)', 'Anti-RSV antibodies', 'Other monoclonal
management of modified	antibodies', 'None of the above'.
-	
SARI episode	Brand name, if anti-RSV antibodies received during hospital stay

Covariate ¹⁷	Description
Treatments received prior to	'Antibiotics', 'Antiviral drug(s)', 'Corticosteroid(s)', 'Anti-RSV
hospital admission for the	antibodies', 'Other monoclonal antibodies', 'None of the above'.
management of current	Brand name, if anti-RSV (or other monoclonal) antibodies
modified SARI episode	received during hospital stay
Medicinal product for the	Binary
prevention of RSV infection	If yes, type ('Antiviral drug', 'Anti-RSV-antibodies', 'Other'),
within 12 months prior to	brand and date (month/year) if anti-RSV-monoclonal antibody
current hospitalisation	
Laboratory results (RSV)	Type of specimen(s), date(s), RSV subtype(s)

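### The optional exclusion for other RSV products pools treatment of the current episode with prophylaxis; removing treated patients takes out almost only cases and can bias that sensitivity analysis

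*Protocol*

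**What the plan says.** Protocol section 11.12.4.2 introduces its list with "Additional sensitivity analyses that can be conducted include". One item is "exclusion of patients who have received monoclonal antibodies and other RSV products for either treatment or pre- or post-exposure prophylaxis prior to hospitalisation", to be done "if there is significant use thereof in the population". The section closes with "All sensitivity analyses will be pre-specified in the SAP".

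The Covariates paragraph of the abstract (section 8) opens with "Variables that are potential confounders and/or effect modifiers will be collected at Study Contributors". Its list includes "history of anti-RSV antibodies received either as prophylaxis", and the entry continues "or treatment for the current or previous modified SARI episodes".

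Table 1 (section 11.9) keeps these exposures apart. One row covers treatment given before admission for the current episode, with anti-RSV antibodies among its options. Another covers treatment during the stay. A third covers preventive RSV products in the preceding 12 months, with type and "brand and date (month/year) if anti-RSV-monoclonal antibody".

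The adjustment set in section 11.12.4 is calendar time, age, sex and comorbidities. RSV treatment is not named there.

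**The concern.** The exclusion joins two exposures that sit at different points in time. Prophylaxis comes before the illness, may itself prevent RSV admission, and may be related to vaccination. Excluding it answers a sensible question.

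Treatment of the current episode comes after vaccination, after infection and normally after an RSV diagnosis. It cannot confound the relation between vaccination and RSV status, because it is a consequence of being a case. The specimen window in sections 11.6.4 and 11.6.5 opens 10 days before admission, so RSV can be diagnosed and treated before the patient is admitted. Controls must be RSV-negative on all molecular samples in that window, so the treated patients will be almost entirely cases.

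At stake is how this one analysis is read. If VE moves after the exclusion, the movement could be put down to other RSV products when the exclusion itself produced it, or it could hide a real effect of prophylaxis. The document is a master protocol from which requestor-specific and site-specific protocols are derived, so the wording is likely to be carried forward.

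**Working it through.** The protocol gives no figure on this point, so there is none to reproduce.

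**Inputs.** From section 11.12.4: VE = (1 − OR) × 100%, with OR the exposure odds ratio. Assumed, because the documents do not give them: true VE of 50%, 70% or 80%; treated shares of cases between 0 and 30%; coverage among controls of 20% or 50%.

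**Formula.** Let q_v and q_u be the shares of vaccinated and unvaccinated cases treated before admission. Suppose that only cases are removed. The odds of vaccination among the remaining cases are the original odds times (1 − q_v)/(1 − q_u), and the odds among controls do not change. Hence

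OR observed = OR true × (1 − q_v)/(1 − q_u).

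**Example in counts.** Take 1,000 controls with 20% coverage: 200 vaccinated and 800 unvaccinated, odds 0.25. With true OR 0.30 the odds among cases are 0.30 × 0.25 = 0.075, for instance 75 vaccinated and 1,000 unvaccinated cases. Remove 10% of the former and 20% of the latter: 67.5 and 800 remain, odds 0.0844. The observed OR is 0.0844/0.25 = 0.3375, so VE is about 66%.

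**Range.**

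| q_v | q_u | Factor | True VE 50% | True VE 70% | True VE 80% |
|---|---|---|---|---|---|
| 20% | 20% | 1.00 | 50.0 | 70.0 | 80.0 |
| 2% | 5% | 1.03 | 48.4 | 69.1 | 79.4 |
| 5% | 10% | 1.06 | 47.2 | 68.3 | 78.9 |
| 10% | 20% | 1.13 | 43.8 | 66.2 | 77.5 |
| 15% | 30% | 1.21 | 39.3 | 63.6 | 75.7 |
| 20% | 10% | 0.89 | 55.6 | 73.3 | 82.2 |

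Results are the same at 20% and 50% coverage. Three things follow. Equal shares leave VE unchanged and cost only cases. The sign depends on which group is treated more often. With low use the shift at a true VE of 70% is about 1 point.

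**If such treatment were used as a covariate.** A logistic model at true VE 70%, with a treatment indicator that is 1 only among cases, separates completely: the treatment coefficient diverges, reaching about 25 to 26 on the log scale when iteration stopped. VE then agrees with the exclusion result: 70.0 at equal shares of 20%, about 66 at 10% and 20%, and 73.3 at 20% and 10%. Such a variable cannot serve as a confounder.

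**The case against.** The best defence is that little depends on this item. It is optional, conditional on significant use, and left to the SAP for pre-specification. It would be read beside the unrestricted estimate. All of that stands, and it makes the point small. It does not remove it: treatment is named in the exclusion rule itself, so this is a stated criterion rather than detail left open for the SAP.

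Three stronger readings are tempting, and the documents do not support them.

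- *That the exclusion necessarily biases VE.* It does so only if treatment differs by vaccination status. Reasons to expect a difference exist: objective 2.5 allows VE to vary by severity, and section 13 says that high-risk groups are often prioritised for vaccination. Both severity and risk could influence who is treated. The documents give no data, and these influences could pull in opposite directions.
- *That only cases can be removed.* Section 11.12.4.2 itself foresees test-negative controls with a positive rapid antigen test before admission, and such a control could have been treated. The criterion also covers prophylaxis, can be read to cover antibodies not directed at RSV, and does not say whether treatment means the current or a previous episode.
- *That the plan adjusts for treatment.* The abstract lists it among variables to be collected, under a label that covers confounders and effect modifiers. No section puts it in a model.

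Nor does the condition on significant use mean that the analysis runs just when the distortion is largest. It refers to all these products together, and prophylaxis alone could meet it.

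**Conclusion.** The point holds as a limited one. Pooling treatment of the current episode with prophylaxis makes this optional analysis select on a consequence of the outcome, and its VE can be biased in either direction. At a true VE of 70%, the shifts range from about 1 point at low use (2% and 5%) to about 6 points downward at 15% and 30%, and about 3 points upward at 20% and 10%. They are larger at a true VE of 50%, where 15% and 30% give 39.3%. Every treated share is an assumption, as is the simplification that no controls are removed. On its natural reading the exclusion concerns only products received before admission, so treatment during the stay plays no part.

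The primary VE is not affected. The abstract's label is wrong for treatment of the current episode, but it is a label in a data-collection list, not an error in a planned model.

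**What to change.** In section 11.12.4.2, limit the exclusion to RSV products received before symptom onset of the current episode, whether as prophylaxis or as treatment of a previous episode. State that patients are not excluded for treatment of the current episode. Simply deleting treatment from the criterion would go too far, because it would keep patients treated with RSV products for an earlier episode, which is an exposure before the present illness.

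In the abstract's covariate list, take treatment for the current episode out of the potential confounders and effect modifiers and keep it as a descriptive variable.

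The cost is mainly wording, since Table 1 already records prevention and current-episode treatment in separate rows. Two small practical points remain. Month and year dates leave the order relative to symptom onset unclear for a few patients, so the SAP should say how they are handled. Table 1, which is only a summary, shows no row for treatment of a previous episode, so it should be confirmed that the full case report form captures what the abstract lists.
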